1. INTRODUCTION
2. STUDY OBJECTIVES
3. STUDY DESIGN
4. PARTICIPANT ENTRY
5. ADVERSE EVENTS
6. ASSESSMENT AND FOLLOW-UP
7. STATISTICS AND DATA ANALYSIS
8. REGULATORY ISSUES
9. STUDY MANAGEMENT
10. PUBLICATION POLICY
11. REFERENCES

STUDY SUMMARY

TITLE Investigating the relationship between the renin angiotensin system and the coagulopathy associated with COVID-19

DESIGN Double blind randomised placebo-controlled trial

AIMS To determine whether RAS inhibition modulates coagulopathy in COVID-19

OUTCOME MEASURES D-dimer

POPULATION Inpatients with COVID-19

ELIGIBILITY Hospitalised, aged 18 or over

DURATION Each subject will be in the study for 30 days. The study is expected to take 6 months

1. INTRODUCTION

1.1 BACKGROUND

Several clinical trials testing blockade of Angiotensin II (AngII) in COVID-19 using angiotensin converting enzyme inhibitors (ACEI) or angiotensin II receptor blockers (ARBs) are underway (e.g. NCT04330300, NCT04335786 and NCT04355936). The rationale for these trials is based on the two predicates. First, SARS-CoV2 will lead to internalisation and inactivation of ACE2 (the enzyme that metabolises AngII to Ang(1-7)) and cause AngII accumulation, as occurred with SARS-CoV1 (Kuba, Lo, Gralinski, Wang). Second, that COVID-19 has many features which are strikingly similar to the effects of excessive exposure to AngII (Tang (a), Tang (b), Whitaker, Gavras (a), Gavras (b)). However, this approach may fail to yield net benefit, because it overlooks the role of Ang(1-7) and the impact of these drugs on Ang(1-7). Ang(1-7) is the product of ACE2 mediated AngII metabolism, and hence the inactivation of ACE2 induced by COVID-19 will lead not only to AngII accumulation, but also to Ang(1-7) depletion. Because this is due specifically to ACE2 inactivation, it does not occur in more classical conditions featuring renin-angiotensin axis activation, such as heart failure. Ang(1-7) functionally antagonises AngII through its agonist action at the MAS receptor, and may also potentially act as a biased agonist at the AngII receptor (AT1R) (Bader, Galandrin, Montezano, Teixeira, Touyz). Indeed, animal models show that Ang(1-7) depletion causes pathology which aligns with that seen in COVID-19 patients, including lung injury, lung inflammation, myocardial microinfarcts, characteristic glomerular thrombosis and coagulopathy. (Bihl, Bossi, Driggin, Fraga Silva, Hao, Klein, Supe, Xue, Yang (a), Yang (b), Zhang K, Zhang X).

The coagulopathy is particularly noteworthy given an early increase in D-dimer has very high positive predictor value for death in COVID-19, and D-dimer concentrations are unusually high in COVID-19, over and above what would be expected for an acute phase response in an unwell patient (Tang (a), Tang (b)). Given the pleiotropic effects of AngII and Ang(1-7) on the components of the coagulation system, overactivation of the renin-angiotensin system may partly drive dysregulation of coagulation. We therefore hypothesise that the coagulopathy associated with COVID-19 is partly explained by both AngII accumulation and Ang(1-7) deficiency. Importantly, whilst ACEI and ARB treatment will antagonise AngII accumulation, they not only fail to address Ang(1-7) deficiency, but would in fact worsen it. This is because ACEI will further deplete Ang(1-7) production, over and above that caused by ACE2 internalization (Luque), and whilst an ARB will not further deplete Ang(1-7), it will prevent it from binding AT1R and hence block its beneficial actions via this receptor. Hence neither ACEi nor ARBs are appropriate tools to address this hypothesis in the context of COVID-19 infection

TRV027 is a similar peptide to Ang(1-7) but is a much more potent biased agonist at AT1R than Ang(1-7), potently and selectively recruiting β -arrestin to the AT1R while antagonizing Ang II-stimulated Gq activation (Violin). This β -arrestin bias of the ligand translates into unique downstream signaling, including extracellular signal-regulated kinases 1 and 2 (ERK1/2) phosphorylation and AT1R internalization. Recruitment of β -arrestin by TRV027 stimulates the activation of endothelial cell nitric oxide synthase (eNOS) and prostacyclin production (Violin). The combination of inhibition of Ang-II-mediated G-protein activation and activation of eNOS and prostacyclin production may contribute to the in vivo vasodilatory properties of TRV027 (Violin). ***In summary, TRV027, a biased agonist at AT1R, would be expected to oppose the effects of AngII accumulation, and functionally correct the Ang(1-7) deficiency.*** Hence it is an appropriate tool to examine the link between RAS activation and coagulopathy in the context of COVID-19 infection.

1.2 HYPOTHESIS

Inhibition of RAS activation by biased agonism of AT1R with TRV027 improves coagulopathy in COVID-19 infection.

1.3. SUMMARY OF RISK MANAGEMENT

TRV027

Non-Clinical Safety

Nonclinical safety pharmacology and toxicology studies have shown that TRV027 is compatible with blood, non-genotoxic, and that continuous IV infusions up to 14 days duration are well tolerated. The no observed adverse effect level (NOAEL) in 2-week continuous IV infusion studies in rats and dogs was 500 µg/kg/min, the highest dose tested. Measured TRV027 plasma concentrations at the NOAEL dose in rats and dogs were approximately 20-times higher than extrapolated steady-state plasma concentrations in humans administered the highest Phase 2 clinical dose of 25 mg/hr.

Clinical Safety

TRV027 has been studied in healthy volunteers (n=20) and in three studies in patients with heart failure. In the FTIH study (NCT01514578), a dose range of 0.01 to 20 µg/kg/min for 4 hours (2.4 to 4800 µg/kg) was studied in 20 healthy subjects; the highest dose was expected to be approximately 20-fold higher than the efficacious dose in acute decompensated heart failure (ADHF) patients. All AEs reported were mild and transient. There were three AEs, in two subjects, that were considered possibly related to study drug: mild fatigue, and mild dizziness and paresthesia. All resolved within 2 hours without medical intervention. There were no deaths, no SAEs, and no AEs that led to discontinuation from the study. There were no clinically significant changes in laboratory findings, vital signs (Heart Rate, Blood pressure, Oxygen saturation, respiratory rate and temperature), ECGs or physical examinations.

Study CP120027.1002 enrolled 17 patients with HF and renal dysfunction. Each patient received both placebo and a dose (1.25-31.25 mg/hr) of TRV027 as a 6.5 hr continuous infusion (NCT01444872). All AEs reported in this study were mild or moderate in nature. There were no serious adverse events or clinically significant adverse events reported.

In CP120027.2001, 33 patients with NYHA class 3-4 heart failure and a clinical indication for right-heart catheterization received either a dose regimen of TRV027 or volume-matched placebo (NCT01187836). The doses studied were as follows:

- Cohort 1: 0.1, 0.2, 0.4, 0.7 µg/kg/min each for 1 hour over hours 1-4, followed by 1 µg /kg/min for 10 hours
- Cohorts 2 and 4: 0.3, 0.6, 1.2, 2.4 µg/kg/min each for 1 hour over hours 1-4, followed by 3 µg/kg/min for 10 hours
- Cohort 3: 1, 2, 4, 8 µg/kg/min each for 1 hr over hours 1-4, followed by 10 µg/kg/min for 10 hours.

There were no serious adverse events attributed to TRV027 treatment. In the first cohort, one subject experienced hypotension necessitating dose reduction and then discontinuation of the study drug infusion. No other TRV027-related clinically significant adverse events were reported.

In the CP120027.2002 study (n= 621 patients with ADHF) which used doses ranging from 1-25 mg/hr for 48-96 hours, no safety issues were identified that affected the safety of trial subjects (NCT01966601). There was no difference from placebo in non-serious and serious treatment-emergent adverse events, events leading to discontinuation, or deaths.

Pharmacokinetics of TRV027

The pharmacokinetics of TRV027 has been studied in healthy volunteers, in patients with stable mild/moderate heart failure, patients with stable NYHA class III/IV CHF, and in 621 adults with acute decompensated heart failure. The clearance of TRV 027 is rapid (ranging between 51.3-127 L/hr) and exhibits a short half-life (4.2-15.8 minutes). Heart failure, sex, or renal dysfunction had no significant effect on the clearance of TRV027. TRV027 is not metabolized by, nor does it inhibit any of the CYP450 enzymes. The plasma protein binding of TRV027 is low at 53.4%.

2. STUDY OBJECTIVES

Primary

To determine whether the coagulopathy associated with COVID-19 infection is driven by over activation of the renin angiotensin system (RAS)

Secondary objective

To investigate whether dysregulation of other systems associated with COVID-19 infection is driven by over activation of the renin angiotensin system (RAS)

3. STUDY DESIGN

The proposed study will be run as a double-blind, randomized controlled experimental medicine study in male and female hospitalised patients (n=60) aged 18 or over, with confirmed COVID-19 infection. Patients who are admitted with confirmed COVID-19 infection will be screened with a routine medical assessment (see Table 1) and enrolled if they meet the eligibility criteria. Subjects will be block randomised based on age to continuous intravenous infusion of placebo or TRV027 for 7 days.

Day 1 procedures can occur on the same day of screening and include a venous blood test prior to commencing an intravenous infusion of either placebo (250ml sodium chloride 0.9%) or TRV027 in 250ml sodium chloride 0.9% at 12mg/hr. The infusions will continue for 7 days. Venous blood tests will be repeated at days 3, 5 and 8 amounting to approximately 120mLs of blood in total over the 8-day period.

Once the infusion has finished, the subjects will remain in hospital for a further 24 hours for vital signs and adverse event monitoring. If the infusion is stopped before the 7-day dosing period finishes, they will be advised to remain in hospital for a 24-hour period for monitoring during which time the study assessments will continue. If discharge is planned for day 6 or 7 the day 8 blood tests can be taken on the day of discharge. They will also be followed up at Day 30 either by telephone call or through examination of medical records.

Table 1: Schedule of Study Events

Study Day	*Screening	*1	2	3	4	5	6	7	8	9	30
Informed consent (or agreement from consultee if incapacitated)	X										
Eligibility assessment; routine medical assessment (history, observations)	X										
Review of Concomitant Medications ¹		X	X	X	X	X	X	X	X		
Pregnancy test (If appropriate)	X										
Venous blood test for primary and exploratory endpoint assessment:											
D-dimer		X		X		X			X		
Platelets		X		X		X			X		
aPTT		X		X		X			X		
INR		X		X		X			X		
Fibrinogen		X		X		X			X		
Plasma Renin Mass		X									
Total Bilirubin		X		X		X			X		
LDH		X		X		X			X		
Haptoglobin		X		X		X			X		
Creatinine		X		X		X			X		
BNP		X		X		X			X		
Troponin		X		X		X			X		
Ferritin		X		X		X			X		
Pro-calcitonin		X		X		X			X		
Glucose		X		X		X			X		
Clinical assessment for exploratory endpoints											
Inotrope requirement		X		X		X			X		
GCS		X		X		X			X		
SOFA score		X		X		X			X		
Randomisation		X									
Infusion		X	X	X	X	X	X	X	X		
Vital signs monitoring four times a day		X	X	X	X	X	X	X	X	X	
Adverse event monitoring		X	X	X	X	X	X	X	X	X	
Telephone call or medical record check											X

[figure not shown]
*Screening and day 1 can be combined

1. All concomitant medications will be reviewed at baseline but only those which affect eligibility or are associated with AEs will be recorded for subsequent days in the Ecrf. ACEi and aldosterone antagonists will be recorded.

Dose Rationale

TRV027 has been studied in patients with acute heart failure in doses ranging from 1.25 – 31.25 mg/hr. Using in vitro-derived AT1R receptor binding data as well as population PK data in healthy volunteers, simulations were performed to explore a range of doses of TRV027 which might be expected to result in at least 80% receptor occupancy, correcting for protein binding. The results (Figure 1) suggest that 12 mg/hr will result in median receptor occupancy well in excess of 80%. This dose is in the mid-range of what has been studied clinically and is expected to be well tolerated.

Figure 1: Estimation of the median AT1R receptor occupancy resulting from TRV027 given at a dose of 12 mg/hr for 96 hours

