3.1 STUDY OUTCOME MEASURES

Primary Endpoint

- Mean change from baseline D-dimer at day 1 to day 3 post randomisation

Exploratory Endpoints

- Assessed on days 1, 3, 5, and 8
 - Markers of dysregulation of coagulation system, e.g.
 - D-dimer, Coagulation profile
 - Markers of dysregulation of RAS, e.g.
 - Renin mass and activity (Day 1 only)
 - Markers of dysregulation of other systems, e.g.
 - SOFA score ((Pa/SaO₂)/FiO₂, GCS, Total bilirubin, platelets, creatinine, BP and inotrope requirement).

- Markers of dysregulation of the endocrine system
 - BNP, Troponin, Ferritin, LDH, Haptoglobin
 - Glucose
- Markers of Inflammation (i.e. Bacterial Sepsis)
 - Pro-calcitonin

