1.3 Study Endpoints

Primary endpoint

Mean change from baseline D-dimer at day 1 to day 3 post randomisation will be compared using paired or unpaired non-parametric methods as appropriate.

Secondary endpoints

Mean change from baseline to day 1 plasma renin and from day 1 to day 3, day 5, day 8 for exploratory variables will be investigated

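### Samples labelled Day 8 may be drawn on Day 6 or 7 at discharge, so the Day 8 exploratory comparison mixes study days and infusion lengths with no rule for actual timing

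*Protocol*

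**What the plan says.** Protocol section 3 sets the infusion length ("The infusions will continue for 7 days") and the sampling days ("Venous blood tests will be repeated at days 3, 5 and 8"). It then allows an exception: "If discharge is planned for day 6 or 7 the day 8 blood tests can be taken on the day of discharge".

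The same paragraph has two sentences about staying in hospital. For a completed infusion: "Once the infusion has finished, the subjects will remain in hospital for a further 24 hours for vital signs and adverse event monitoring". For an infusion stopped early, patients are told that "they will be advised to remain in hospital for a 24-hour period for monitoring during which time the study assessments will continue". Table 1 marks both infusion and blood tests on Day 8 and does not say which comes first.

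Protocol 3.1 lists Days 1, 3, 5 and 8 for the exploratory endpoints. SAP 1.3 places the change "from day 1 to day 3, day 5, day 8 for exploratory variables will be investigated" under its secondary endpoints, and SAP 3.3 compares the arms on those changes. Neither document gives a Day 8 window, a flag for early samples, an analysis by actual day or a related sensitivity analysis. SAP Tables 10 and 11 have columns for Days 1 and 3 only, so the Day 8 comparison is planned in the text without a table to hold it.

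The primary endpoint is "Mean change from baseline D-dimer at day 1 to day 3 post randomisation".

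**The concern.** A discharge sample from Day 6 and a sample taken at the end of a full infusion on Day 8 are different measurements. They belong to different days of the illness and follow different amounts of drug. They may also differ in whether the infusion was running when blood was taken. The plan gives them one label and compares the arms on it.

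The sampling day is not set by the schedule. Planned discharge sets it, and discharge happens after randomisation. It is reasonable to infer that patients who recover faster are sampled earlier, although the documents give no discharge figures. If the drug changes the speed of recovery, the mix of sampling days will differ between arms.

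Day 8 is the only scheduled sample that reaches the end of the 7-day infusion. It carries information for the secondary objective and on the later course of D-dimer, so its meaning should be fixed before the comparison is run.

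**Working it through.** **The plan's own figure.** The only design calculation is 30 per group for 80% power at alpha 0.05 to detect a 30% change in D-dimer (Protocol section 7). It gives no standard deviation, so it cannot be reproduced. It concerns D-dimer without any Day 8 target, and nothing below depends on it except the scale comparison in step 4.

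**1. Infusion received before the sample.** Inputs: 7 days of infusion = 168 h; sampling on Day 6, 7 or 8 (Protocol section 3). Assumption: infusion starts on Day 1 and samples fall at the same clock time, so maximum hours = (day − 1) × 24. If the infusion stops 24 h before discharge, subtract 24.

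| Actual day of the sample labelled Day 8 | Infusion runs until the sample | Stopped 24 h before the sample |
|---|---|---|
| 6 | 120 h (120/168 = 71%) | 96 h (57%) |
| 7 | 144 h (144/168 = 86%) | 120 h (71%) |
| 8, full course | 168 h (100%) | not applicable |

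The right-hand column applies only if the advice to stay is followed in full.

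**2. Drug present at sampling.** Protocol 1.3 gives a half-life of 4.2 to 15.8 minutes. Five half-lives take 5 × 4.2 = 21 to 5 × 15.8 = 79 minutes. A sample taken 24 h after the stop therefore has essentially no drug in plasma. The same uncertainty affects full-course patients on a smaller scale, because Table 1 does not order the Day 8 sample and the end of infusion.

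**3. Average exposure at Day 8.** Assume that a share f of samples is early and that d infusion days are lost. Mean exposure is then 1 − f × d/7. With f = 10% and d = 1 this is 99% of plan; with f = 50% and d = 3 it is 79%.

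**4. Possible shift between arms.** Assume that the marker falls by a fraction b per day, that the arms differ by Δ in the share sampled early, and that early samples are m days early. The log ratio shifts by −ln(1 − b) × Δ × m.

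| b | Δ | m | Log shift | Ratio |
|---|---|---|---|---|
| 5% | 10 points | 1 | 0.005 | 1.005 |
| 10% | 20 points | 1 | 0.021 | 1.021 |
| 10% | 30 points | 2 | 0.063 | 1.065 |
| 15% | 20 points | 2 | 0.065 | 1.067 |
| any | 0 | any | 0 | 1.000 |

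All of b, Δ and m are assumed, and larger inputs give larger shifts. With a falling marker, the arm with more early samples looks higher. With a rising marker, it looks lower.

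For scale, n = 30 per group with a ratio of 0.70 and a two-sided test implies a log SD of 0.357 / [(1.960 + 0.842) × √(2/30)] = 0.493. The standard error is 0.493 × √(2/30) = 0.127. If that SD held at Day 8, the shifts in the table would be about 0.04 to 0.5 standard errors.

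**5. Who is analysed.** SAP 2.2 limits the Full Analysis Set (FAS) to patients who received the full course, but puts in the incomplete set only those who did not complete 3 days. SAP 3.5 counts 72 h as 100% for the primary endpoint. If the full course means 7 days, patients discharged on Day 6 or 7 leave the FAS; the mixing disappears and is replaced by selection on recovery. If it means 72 h, they stay and the mixing occurs. The documents do not settle which.

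**The case against.** The strongest reply is that little depends on this. The measures are exploratory in the protocol, the primary endpoint is at Day 3, and the rule is the same in both blinded arms. If the drug affects neither discharge nor the markers, the expected shift is zero and no false positive arises. The assumed shifts are small beside the 30% design effect. The discharge rule also has a virtue, because it secures a last sample from patients who would otherwise have none. Lost exposure is partly visible, since SAP 3.5 and Table 2 report dose completion and, by arm, infusion missed through discharge. The case report form is not among the documents, so sampling and stop times may already be recorded. All of this stands. It limits the size of the point, but it does not supply a rule for the actual sampling day.

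A reader might infer more than the documents support:

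- **That off-drug samples have lost any drug effect.** The half-life describes plasma drug. The documents do not say how fast D-dimer, ferritin or BNP would return after stopping, so a count of half-lives does not measure bias in a marker.
- **That the comparison is biased against TRV027.** This needs earlier discharge on the drug and a falling marker; neither is known.
- **That the discharge sentence flatly contradicts the 24-hour stay.** A Day 6 or 7 discharge means an early stop, and the sentence on early stops gives advice. The two are in tension and need reconciling, but compliance with both is possible.
- **That Day 6 and 7 values should be barred.** This would exchange mixing for missing data that depend on recovery.

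**Conclusion.** The point holds as a limited flaw in the Day 8 exploratory and secondary comparisons. From the protocol's own timings, one label can cover up to two study days and infusion of 120 to 168 h, or as little as 96 h if the 24-hour stay is observed. Whether the drug is still running at sampling is undefined. The certain consequences are added noise and mixed exposure, provided that some patients are discharged on Day 6 or 7 and remain in the analysis set. Bias between arms is conditional on different discharge timing or different time trends by arm: about 0.5–7% on the ratio scale under the assumed inputs, and zero when both are equal. A reader might suppose that the trial's main result is affected; it is not, because the Day 3 endpoint and the sample size do not use this sample. The correction is cheap and worth making before the Day 8 data are compared.

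**What to change.** - **Protocol section 3.** Keep the discharge sample. Where the stop is planned, draw the sample before the infusion is stopped. Record the actual sample time and the infusion stop time. State for Day 8 itself whether blood is taken before or after the infusion ends.
- **SAP 1.3 and 3.3.** Label an early sample as end-of-infusion/discharge. Analyse the late samples by actual study day, for example with the log marker as outcome and actual day as the time variable, using all samples. Add a sensitivity analysis restricted to samples truly taken on Day 8. This should support the main analysis and not replace it, because it leaves out patients discharged early.
- **SAP 2.2.** State whether patients discharged on Day 6 or 7 belong to the FAS, and define the full course consistently with the 3-day and 72-hour cut-offs.
- **For the sponsor.** Reconcile the discharge sentence with the two 24-hour-stay sentences in Protocol section 3.

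The cost is two recorded times, if they are not already captured, slightly more analysis, and fewer values in the strict Day 8 sensitivity analysis. Analysis by actual day removes the mislabelling. It does not remove the dependence of sampling on recovery, so the number of early samples should be reported by arm.

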3.1 STUDY OUTCOME MEASURES

Primary Endpoint

- Mean change from baseline D-dimer at day 1 to day 3 post randomisation

Exploratory Endpoints

- Assessed on days 1, 3, 5, and 8
 - Markers of dysregulation of coagulation system, e.g.
 - D-dimer, Coagulation profile
 - Markers of dysregulation of RAS, e.g.
 - Renin mass and activity (Day 1 only)
 - Markers of dysregulation of other systems, e.g.
 - SOFA score ((Pa/SaO₂)/FiO₂, GCS, Total bilirubin, platelets, creatinine, BP and inotrope requirement).

- Markers of dysregulation of the endocrine system
 - BNP, Troponin, Ferritin, LDH, Haptoglobin
 - Glucose
- Markers of Inflammation (i.e. Bacterial Sepsis)
 - Pro-calcitonin

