3.3 Exploratory data

Exploratory data variables will be measured at baseline and at days 3,5 and 8 (Tables 9, 11). Differences in exploratory variables will be calculated for each patient, enabling an estimate of the mean difference and 95% confidence interval to be calculated for each treatment arm. The differences for the treatment groups will be compared using parametric or non-parametric tests as appropriate.

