3.7 Additional data

Vital signs and cardiovascular monitoring will be documented at days 1, 3 and 5. (Table 12).

Table 1. Baseline characteristics

	FAS		IAS	
	Control	TRV027	Control	TRV027
	Median (range) or N (%)			
Age (yr)				
Age group				
<60				
60-69				
>69				
Gender				
Male				
Female				
BMI (kg/m²)				
Ethnicity				
White				
Mixed				
Asian				
Black				
Other				
Disease severity?				
Ie FDA grade 1-5?				

Table 2 Drug Compliance

	Control N (%)	TRV027 N (%)
Total Missed doses		
Total % Compliance		
Median missed doses per patient (range)		
Patients with missed dose due to hospital discharge		
Patients with missed dose due to death		

Table 3 Safety data – Pooled Adverse events

	Control		TRV-027	
	No. of Events	No. of Subjects*	No. of Events	No. of Subjects*
Number of Adverse events				
Severity				
Grade 1				
Grade 2				
Grade 3				
Grade 4				
Grade 5				
Missing				
AE classification				
Not serious				
Serious				
AE expectedness				
Expected				
Unexpected				
Not Applicable				
Missing				
Relation to study				
Definitely				
Probably				
Possibly				
Unlikely				
Not related				
Not assessable				
Missing				

* A patient may have several AEs

Table 4 – TRV027 Safety data –Adverse events details by patient

Control				TRV-027			
Pt ID	AE category	AE name	Grade	Pt ID	AE category	AE name	Grade

Table 6 Safety data – Serious Adverse Events

	Control		TRV027	
	No. of Events	No. of Subjects	No. of Events	No. of Subjects
Number of Serious Adverse Events				
Reasons for SAE				
Resulted in death				
Life threatening				
Congenital anomaly/birth defect				
Persistent or significant				
Disability/incapacity				
Inpatient hospitalisation/prolongation of existing				
Other				
Severity				
Mild				
Moderate				
Severe				
Life threatening				
Death				
Causal relationship to study drug				
Definitely				
Probably				
Possibly				
Unlikely				
Not related				
Not assessable				

Table 7 Safety data – Serious Adverse events details (Controls)

SAE description	SAE Term	Outcome

Table 8 Safety data – Serious Adverse events details (TRV027)

SAE description	SAE Term	Outcome

Table 9 Day 30 Survival

	Control	TRV027
Alive		
Dead		
Lost to follow-up		

Table 10 FAS Efficacy and exploratory parameters

	Control			TRV027		
	Day 1 [N=] Median (range)	Day 3 [N=] Median (range)	Difference D3 – D1	Day 1 [N=] Median (range)	Day 3 [N=] Median (range)	Difference D3 – D1
D-dimer						
Platelets						
aPTT						
INR						
Fibrinogen						

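### Inotrope support is assessed on Days 1, 3, 5 and 8 with no look-back window and tabulated only for Days 1 and 3, so support between assessments or outside the FAS is not counted as an outcome by arm

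*Protocol*

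**What the plan says.** Protocol 3.1 introduces the exploratory endpoints with "Assessed on days 1, 3, 5, and 8" and places "creatinine, BP and inotrope requirement" within the SOFA score. Protocol Table 1 also has a separate row, "Inotrope requirement", marked on those four days and blank on Days 2, 4, 6, 7 and 9. Neither place defines the period that an entry covers. On treatment length, Protocol section 3 says "The infusions will continue for 7 days".

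SAP 3.3 reads "Exploratory data variables will be measured at baseline and at days 3,5 and 8 (Tables 9, 11" (closing bracket omitted here). The first of those two tables is "Table 9 Day 30 Survival", which has no place for inotropes. The second, Table 11, shows inotrope requirement as Yes/No percentages under Day 1 and Day 3, with no Day 5 or Day 8 column.

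SAP 2.2 makes the Full Analysis Set (FAS), defined by receipt of the whole course, the population for analysis. Patients infused for less than 3 days contribute baseline data and descriptive summaries. SAP 2.5 says that withdrawn patients remain in the final analysis.

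For drugs started after baseline, footnote 1 to Protocol Table 1 says that "only those which affect eligibility or are associated with AEs will be recorded for subsequent days in the Ecrf".

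**The concern.** The protocol's background section describes signalling effects that "may contribute to the in vivo vasodilatory properties of TRV027". Protocol 1.3 reports one earlier subject whose hypotension led to dose reduction and then discontinuation, and a half-life of 4.2 to 15.8 minutes. Five half-lives are 5 × 4.2 = 21 minutes to 5 × 15.8 = 79 minutes. If the drug did create a need for circulatory support, that need could be brief and could end soon after the infusion was changed. Intermittent prevalence detects this pattern least well.

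The planned summary has three weaknesses as a comparison of arms:
- It can miss episodes between assessment days.
- It does not separate new starters from patients already supported on Day 1.
- A patient whose infusion stopped early can drop out of the table altogether.

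A similar Day 3 percentage in the two arms would therefore be weak reassurance about new circulatory support over the 7-day infusion.

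**Working it through.** The documents give no figure for inotrope use, so there is no stated number to reproduce. The only design figure, 30 per group for D-dimer, does not bear on this point.

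**Inputs from the documents.** Infusion of 7 days = 168 h; assessments on Days 3, 5 and 8 (Protocol 3 and 3.1); tabulated post-baseline day: Day 3 only (SAP Table 11).

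**Assumptions, not in the documents.** One episode of length L hours, with onset uniform over 0 to 168 h. Infusion start is uniform between 08:00 and 20:00, a mean clock hour of 14.

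**Point-in-time reading** at 48, 96 and 168 h. Each reading catches onsets in the L hours before it. For L up to 48, capture is 3L/168 on the full schedule and L/168 for Day 3 alone.

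**Calendar-day reading** (any use on that date). Day 3 and Day 5 each catch an onset window of 24 + L hours. Day 8 catches on average 14 + L, because onset is limited to 168 h. For L up to 24, capture is (62 + 3L)/168 on the full schedule and (24 + L)/168 for Day 3 alone. At L = 48 the windows join and cover all onsets. The Day 3 window is then cut off at infusion start, leaving on average 72 − 14 = 58 h.

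| Episode length | Days 3, 5, 8: point | Days 3, 5, 8: calendar day | Day 3 only: point | Day 3 only: calendar day |
|---|---|---|---|---|
| 6 h | 18/168 = 11% | 80/168 = 48% | 6/168 = 4% | 30/168 = 18% |
| 12 h | 36/168 = 21% | 98/168 = 58% | 12/168 = 7% | 36/168 = 21% |
| 24 h | 72/168 = 43% | 134/168 = 80% | 24/168 = 14% | 48/168 = 29% |
| 48 h | 144/168 = 86% | 100% | 48/168 = 29% | 58/168 = 35% |

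**Sensitivity to the look-back window.** If each entry covered the preceding 24 h, capture on Days 3, 5 and 8 would be 54%, 64%, 86% and 100% for the four lengths. If each entry covered all time since the last assessment, the full schedule would miss nothing. Episodes of 72 h or more cannot be missed on the full schedule under any reading.

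**Limit of the Day 3 column.** An episode that starts after Day 3 cannot appear there, whatever its length. Even if Day 3 runs to hour 72, (168 − 72)/168 = 57% of the infusion period lies beyond it.

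**Analysis set.** SAP 3.5 counts 72 h of infusion as complete for the primary endpoint, so the whole course in SAP 2.2 could mean 72 h or 7 days. On either reading, a patient stopped before 72 h is outside the FAS. Table 11 names no population of its own, so SAP 2.2 governs unless SAP 2.5 overrides it. The two sections need reconciling.

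**The case against.** The strongest reply is that the endpoint is not the only net:
- Protocol 5.2 records adverse events continuously from consent to 24 h after the infusion and includes clinically important events of any kind.
- Protocol 5.1 treats life-threatening events, and those needing intervention to avert a serious outcome, as serious.
- Concomitant drugs are reviewed on each of Days 1 to 8, and those linked to an adverse event are recorded.
- The SAP lists adverse events by patient and arm, summarises serious ones, and reports dosing interruptions for each patient.
- A safety committee looks at safety data and endpoints after every 12 recruits.

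A reader might infer that support between visits is never counted. These routes show that this goes too far. They are not systematic, however. Protocol 5.2 leaves other events to medical judgement, does not record routine observations separately as adverse events, and normally disregards known COVID-19 symptoms. None of the SAP tables available for review counts new inotrope use by arm.

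Three other strong readings also fail:
- That each entry is a momentary snapshot is an inference, because the window is undefined.
- That this is the only organ-support outcome tabulated cannot be verified, because Table 12 breaks off and Table 5 is absent from the text available.
- That inotrope use is the clearest sign of harm has no support. The hypotension case mentions no inotrope, and Protocol 1.3 reports no difference from placebo in adverse events in the 621-patient study.

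It is also fair that inotrope requirement serves as an exploratory SOFA component timed with the blood tests, so counting new use adds a question. Early deaths leave the table because of the FAS definition rather than the visit schedule, and SAP Table 9 shows deaths to Day 30 by arm. These points limit the concern but do not remove it.

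**Conclusion.** The point stands as a gap in measurement and reporting. The period covered by each inotrope entry is undefined, SAP Table 11 omits two of the three post-baseline days that SAP 3.3 names, and no planned outcome counts new support by arm among everyone infused.

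The loss is large for short episodes in the table as laid out: 79% to 93% of 12 h episodes would not appear in the Day 3 column. It is small for long episodes on the full schedule, at most 14% at 48 h. These rates rest on uniform onset and assumed durations. With no event rate given, the number of episodes missed among 60 patients cannot be estimated.

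A reader might go on to infer that the plan conceals harm from TRV027. The documents do not support that. They show only that equal percentages would be weak evidence of no difference. The measure is exploratory and safety-related, so this is a worthwhile inexpensive improvement.

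**What to change.** 1. Record the start and stop date and time of any inotrope or vasopressor from Day 1 to 24 h after the infusion ends. State explicitly that both classes count, since the documents name only inotropes.
2. Add to SAP Table 11 a row for *any inotrope or vasopressor started after the infusion began*, by arm, among all infused patients not on one at Day 1. Show deaths in the same window beside it.
3. Keep the prevalence row, state the period each entry covers, and give it columns for Days 1, 3, 5 and 8 to match SAP 3.3. Correct the reference to Table 9.

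The cost is a little more data entry and one table row that uses all infused patients instead of the FAS. SAP 2.3 says that data are transcribed into REDCap from sources such as the electronic medical record, so the times can be taken from there, retrospectively if need be. No clinical procedure changes.
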